5.1.1.1 Sensitivity Analysis

Sensitivity analysis for the CGI-S A/A will focus on the following areas:

Estimate over 8-12 week visits

To assess the degree to which estimating across visits represents the overall effect observed, the primary analysis will be repeated for visits 8, 10, and 12 separately. The combined estimate approach will be revisited if the individual visit analyses are not directionally consistent or if this approach is determined to change the direction of the outcome effect, i.e. one visit is driving the overall effect in the primary analysis (ex: one visit significantly favors treatment, while the other two show no effect or favor placebo).

Analysis Population

The primary analysis will be repeated using the PPS for descriptive purposes only.

Missing Values: Multiple Imputation

To conduct further sensitivity analysis intercurrent events like discontinuation of treatment or patient withdrawal, will be imputed. The PROC MI procedure in SAS will be used to do predictive mean matching using linear regression models ([2]). Imputation will be performed after window mapping. The data at each week will be predicted only using data from the previous weeks. The following SAS model will be used:

```
proc mi data=manual nimpute=30 out=MI1 seed= 123456;
  class trt;
  var trt baseline week2 week4 week6 week8 week10 week12;
  fcs regpmm (week2 = baseline trt baseline*trt /details);
  fcs regpmm (week4 = baseline trt baseline*trt week2 week2*trt /details);
  fcs regpmm (week6 = baseline trt baseline*trt week2 week2*trt week4 week4*trt
/details);
  fcs regpmm (week8 = baseline trt baseline*trt week2 week2*trt week4 week4*trt
week6 week6*trt /details);
  fcs regpmm (week10 = baseline trt baseline*trt week2 week2*trt week4 week4*trt
week6 week6*trt week8 week8*trt /details);
  fcs regpmm (week12 = baseline trt baseline*trt week2 week2*trt week4 week4*trt
week6 week6*trt week8 week8*trt week10 week10*trt /details);
run;
```

Here, baseline is the baseline measurement, and week x is the result of the measurement for Week x . Trt is an indicator variable for the received treatment.

Imputed values that fall outside of the possible range of the test variable will be set to the min or max possible score for the test before imputation.

The following simplifications will be attempted if the model fails to converge for any reason:

1. Only the results from the directly preceding visit and baseline will be used in each of the models (i.e., Week 10 values will be predicted using Week 8 and baseline measurements)
2. Only baseline and baseline*trt will be used in each prediction model

Change from baseline to *Weeks 8- 12* will be calculated for each of the 30 simulated datasets. The main analysis model described in 5.1.1 will be run for each simulated dataset and the values will be aggregated using PROC MIANALYZE. In addition to the estimates for the contrast between treatments at *Weeks 8- 12* (including confidence intervals and p-values), the composition of the total variance in parameter estimation will be broken down by variability between datasets and variability within datasets.

This analysis above will be performed using the entire dataset for imputation across treatment as well as imputation based on the placebo group only.

A tipping point analysis as implemented in Ratitch et al. [3] will also be run. This analysis finds a tipping point across a spectrum of assumptions underlying the missingness of the data (from less conservative to more conservative) in which the conclusion of the study changes from favoring the treatment group to being unfavorable.

Impact of Covariables

The impact of additional covariables will be investigated by including them in the main model, including interactions with Visit and Treatment Arm, as well as the triple interaction between the covariable, Visit and Treatment arm.

The following covariables will be considered:

- Country or center (if number of patients per center allows)
- Psychotherapy at baseline (the main effect is already part of the standard model, so only the interactions need to be added for sensitivity)
- Sex

Other demographic variables may be investigated for sensitivity analysis if there is a reason to suspect an imbalance between treatment arms.

These covariables will be tested by including only one covariable (and interactions) at a time, not all at once. F-tests will be performed for the main effect as well as interactions. In case of highly significant interactions further analysis will be considered. This sensitivity analysis will be performed using the FAS.

Model Assumptions

As described in Section 5.1.1 the assumptions of the mixed model will be investigated visually by the statistician. Regardless of the outcome of this investigation, at least the following sensitivity analyses will be performed:

- A Welch's t-test of the changes from baseline at *Week 12* between treatments without any adjustment for covariables

This sensitivity analysis will be performed using the PPS.

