4.12 Multiple Comparisons/Multiplicity

There are two primary endpoints for efficacy analysis: CGI S A/A and BPDCL, a significant difference in either one is considered sufficient for study success. The overall significance level of the study is thus strictly controlled at a level of 5%. The Hochberg correction will be applied. If one endpoint is below the 2.5% level or if both endpoints are below the 5% level of significance the study is declared a success.

5 Efficacy Evaluation

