Sites with less than two study participants per arm will be pooled. To pool sites: sites with less than two study participants per arm will be ranked within country by the number of participants within the placebo arm (higher numbers are ranked higher). Ranked sites will be pooled starting by pooling the highest ranks until the study participant requirement per arm is met. If more sites are present after the pooling criterion is met the remaining sites are pooled to meet the criterion. In the event that remaining sites do not meet the criterion they will be combined with the previously pooled group. In the event of a tie for ranking the sites, the site with the largest number in the active arm will be used. If the tie persists the sites will be ordered alphabetically or numerically (A and higher number result in a higher rank). Due to the small sample size the interim analysis will be ranked across all sites for pooling as opposed to within country.

Pooling at interim will not include country due to the small number of individuals.

The primary treatment contrast will be based on the LS means from the treatment by visit interaction term. A contrast statement will be written such that model estimates from assessments collected between weeks 8-12 are averaged to compare drug vs placebo.

The test will be a two-sided test of the null hypothesis of no difference between active treatment and placebo at *Weeks 8-12*.

A listing by subject of the CGI-S A/A scores including changes from baseline will be provided.

Individuals with no post-baseline information will have the first post-baseline visit imputed. Individuals reported to drop out for lack of efficacy will be given the baseline placebo mean. Individuals reported as dropping out for any other reason will be given the baseline group mean of their corresponding treatment.

Reasons not associated with lack of efficacy include but are not limited to the following:

- Participant Decision Due to COVID
- Lost to Follow-up
- Adverse Event
- Protocol Deviation
- Physician Decision
- Non-Compliance
- Blood Value During Randomization Visit Was Exclusionary
- Withdrawal by Subject

For the primary efficacy analyses all other missing data will be accounted for using the MMRM estimates.

The analysis of Total BPDCL will not include a categorical summary table.

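### SAP 5.1.1.1 leaves the primary Weeks 8-12 contrast open to change after the per-visit treatment results are known, so strict 5% error control is not guaranteed as written

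*SAP*

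**What the plan says.** SAP 5.1.1 defines the primary contrast: "A contrast statement will be written such that model estimates from assessments collected between weeks 8-12 are averaged to compare drug vs placebo". The ESTIMATE code in the same section gives the three visits equal weights. The hypothesis is two-sided: "The test will be a two-sided test of the null hypothesis of no difference between active treatment and placebo at" Weeks 8-12. SAP 5.1.2 applies the same analysis to BPDCL.

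SAP 4.12 sets the decision rule under Hochberg: "If one endpoint is below the 2.5% level or if both endpoints are below the 5% level of significance the study is declared a success". It also claims: "The overall significance level of the study is thus strictly controlled at a level of 5" per cent.

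SAP 5.1.1.1, under the sub-heading on estimating over the 8-12 week visits, adds that "the primary analysis will be repeated for visits 8, 10, and 12 separately" (meaning Weeks 8, 10 and 12, as SAP 4.6 makes clear). It continues: "The combined estimate approach will be revisited if the individual visit analyses are not directionally consistent". A second trigger follows, for the case where one visit drives the overall effect, with this illustration: "ex: one visit significantly favors treatment, while the other two show no effect or favor placebo".

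SAP 4.6 lists the same per-visit analyses as sensitivity analyses and contains no provision for revisiting anything.

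**The concern.** The clause sits under sensitivity analysis, but what it says will be revisited is the confirmatory estimator. Its triggers are treatment comparisons at individual visits, so they cannot be known until the data are unblinded. SAP 4.8 excludes sensitivity analyses at the interim, so the clause acts on the final results.

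Hochberg controls the familywise error when each endpoint contributes one valid p-value from a contrast fixed in advance, or from a fully specified rule for choosing it. Here the rule has a trigger and no stated consequence. The missing pieces are the replacement contrast, the decision-maker, the level, and whether the averaged p-value still stands.

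What is at stake is the standing of the result. SAP 4.7 explains that the trial moved from 10% to 5% overall error to meet registration requirements. An open choice of primary contrast after unblinding works against that aim. It also leaves a genuine win on the averaged contrast open to dispute whenever the three visits look uneven.

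**Working it through.** **1. The plan's own figure.** SAP 4.7 gives 75 completers per arm for effect size 0.51, two-sided alpha 0.025 and 80% power. The normal formula is n = 2(z₀.₉₈₇₅ + z₀.₈₀)²/d² = 2(2.241 + 0.842)²/0.51² = 73.1, so 74. The t-test version gives 74.4, so 75, with power 80.4%. Then 75/0.8 = 93.75, so 94 per arm and 188 in total. The figure reproduces, and this point does not touch it.

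**2. How often the direction trigger fires under no effect.** The documents give no between-visit correlation, so I assume a common value ρ of 0.5 to 0.8. For three equicorrelated normal statistics, P(signs not all equal) = 3/4 − 3·arcsin(ρ)/(2π). This gives 50%, 44%, 38% and 31% for ρ = 0.5, 0.6, 0.7 and 0.8. Frequent firing does not by itself mean large inflation, as step 3 shows.

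**3. Error per endpoint.** Draw three visit z-scores under the null (2,000,000 draws per setting). The averaged contrast is their mean divided by √((1 + 2ρ)/3). Use the average unless a trigger fires, and otherwise apply the assumed replacement rule. The direction trigger is unequal signs. The second trigger is read as exactly one visit significant for treatment; that is an interpretation, because the SAP gives only an example. One-sided error at nominal 2.5%:

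| Assumed meaning of revisiting | ρ=0.5 | 0.6 | 0.7 | 0.8 |
|---|---|---|---|---|
| Both triggers; best of average or any visit | 6.4% | 6.0% | 5.4% | 4.8% |
| Direction trigger only; best of average or any visit | 3.7% | 3.1% | 2.7% | 2.5% |
| Both triggers; Week 12 replaces the average | 3.0% | 2.9% | 2.8% | 2.8% |
| Can only withdraw a positive claim | ≤2.5% | ≤2.5% | ≤2.5% | ≤2.5% |

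Most of the possible inflation comes from the second trigger combined with free choice of visit. When correlation is high, a visit extreme enough to be significant is rarely accompanied by one of opposite sign, so the direction trigger alone adds little.

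**4. Familywise error under the actual Hochberg rule.** The claim in SAP 4.12 is familywise and two-sided, so the check was repeated for two endpoints by three visits (1,000,000 null trials per setting). Between-visit correlation was 0.5 to 0.9 and between-endpoint correlation 0 to 0.5, both assumed. The second trigger was exactly one visit with p<0.05, and the interim adaptation was not modelled.

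| Rule | Familywise error |
|---|---|
| Averaged contrast locked | 4.8-5.0% |
| Best single visit replaces it, direction trigger only | 4.8-6.9% |
| Best single visit replaces it, both triggers | 6.8-12.9% |
| Week 12 replaces it, direction trigger only | 4.8-5.6% |
| Week 12 replaces it, both triggers | 5.4-6.4% |
| Can only withdraw a positive claim, both triggers | 3.1-4.9% |

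The SAP does not say which row applies.

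**The case against.** The best defence is that the clause is a safeguard. It appears under sensitivity analysis, its stated purpose is to check whether averaging represents the overall effect, and its only example is a combined result carried by one visit while the others show nothing or favour placebo. Read that way, revisiting could only downgrade a win, and there is no inflation. The average is also fixed consistently in the endpoints (SAP 3.2), the estimand (SAP 4.6) and the contrast text and code (SAP 5.1.1). Protocol 9.5 foresees SAP amendments before unblinding and requires deviations after database lock to be documented and justified, so a switch would be visible.

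Much of this stands. A reader might infer that the SAP authorises picking the most favourable visit, that error control is removed outright, or that the false-positive rate about doubles. The documents support none of these. No sentence allows selection of a visit, and the doubling needs both triggers plus free choice of the best result.

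What does not stand is that this settles the matter. The conservative reading is not written down, Protocol 9.5 requires disclosure but does not limit the choice, and SAP 4.6 is silent on revisiting.

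**Conclusion.** The point holds in a limited form. The SAP attaches an unspecified change of the confirmatory contrast to unblinded per-visit results, so the actual error rate cannot be worked out from the text and strict 5% control is not guaranteed.

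No single inflated figure can be attributed to the plan. The per-endpoint range runs from at or below nominal to about 6.4% one-sided at nominal 2.5%. Where the trial falls in it depends on the missing replacement rule, on how the second trigger is read, and on correlations the documents do not supply. That the rule is incomplete is certain from the text; that the error is inflated is not. The correction is still needed before final unblinding, because a clarification made afterwards cannot restore pre-specification.

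**What to change.** Delete the sentence in SAP 5.1.1.1 that provides for revisiting the combined estimate. In its place state, for both CGI-S A/A and BPDCL, that the equally weighted Weeks 8/10/12 contrast is the sole confirmatory test whatever the separate visits show. Add that the per-visit analyses are descriptive and inform interpretation only, which brings the section into line with SAP 4.6.

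The cost is one or two sentences in an SAP amendment dated before final unblinding. No data collection, sample size or power changes. With the contrast locked, familywise error is 4.8-5.0% over the assumed correlations, before any effect of the interim adaptation, which these calculations leave out.

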The estimator for the primary estimand is a likelihood-based mixed model for repeated measures (MMRM). The primary analysis will include all available assessments. Individuals with no post-baseline information will have the first post-baseline visit imputed. Individuals reported to drop out for lack of efficacy will be given the baseline placebo mean. Individuals reported as dropping out for any other reason will be given the baseline group mean of their corresponding treatment.

5. *Sensitivity analyses and missing data.*

To assess the effect of averaging efficacy for visits corresponding to weeks 8-12 on the primary outcome, a sensitivity analysis will be implemented in which the primary efficacy analysis will be run for visits associated with weeks 8, 10, and 12 separately. As clinical studies are limited in the ability to schedule visits on the exact prespecified study day a continuous time model that extracts the predicted estimates on the prespecified study day will be used as a sensitivity model to assess the degree to which windowing affects the outcome. Additional sensitivity models will be run with multiple imputation within each treatment arm. The first analysis (missing at random; MAR) is meant to estimate the treatment effect if all study participants continued on their current trajectory within the treatment group by imputing the missing data within associated treatment groups. The second analysis (missing not at random; MNAR) imputation is performed for all study participants relative to the placebo group only. This analysis assumes study participants at dropout progress similarly to the placebo group. This analysis will provide a lower bound estimate of the effect. A tipping point analysis using multiple imputation will also be performed.

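### The multiple-imputation sensitivity analyses do not separate missed visits from dropout, so the placebo-based run pulls slightly further toward no effect than its stated assumption implies

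*SAP*

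**What the plan says.** SAP 5.1.1.1 gives the purpose of the multiple imputation: "intercurrent events like discontinuation of treatment or patient withdrawal, will be imputed". It then sets the predictor rule, "The data at each week will be predicted only using data from the previous weeks", and prints one PROC MI step with six models, for Weeks 2 to 12. All six follow the rule. The Week 10 model, for example, begins "fcs regpmm (week10 = baseline trt baseline*trt week2 week2*trt week4 week4*trt", goes on to Weeks 6 and 8, and has no Week 12 term. The step fills any missing cell from Week 2 to Week 12. No line of code or text treats a gap that is followed by an observed score differently from the weeks after dropout.

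The section then asks for two runs: "This analysis above will be performed using the entire dataset for imputation across treatment as well as imputation based on the placebo group only". SAP 4.6 describes them. The missing-at-random (MAR) run works "by imputing the missing data within associated treatment groups". In the missing-not-at-random (MNAR) run, "imputation is performed for all study participants relative to the placebo group only", and its meaning is given as: "This analysis assumes study participants at dropout progress similarly to the placebo group". SAP 4.6 presents the MNAR result as a lower bound for the effect and adds a tipping point analysis that also uses multiple imputation. No code is printed for the placebo-based run.

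For the estimand, SAP 4.6 uses a treatment policy strategy for intercurrent events and keeps a hypothetical strategy for early study termination. The primary MMRM uses every available assessment (SAP 4.6 and 5.1.1).

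**The concern.** A vafidemstat participant who misses Week 10 but is rated at Week 12 has not dropped out. Under the printed rule, that participant's Week 10 score is imputed without the Week 12 rating, whereas the MMRM uses the rating through the within-patient covariance. In the placebo-based run, the same gap is filled from the placebo regression. Neither the dropout assumption in SAP 4.6 nor the hypothetical strategy for early termination calls for that.

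The runs are meant to show how far the result depends on what is assumed after dropout. As specified, the placebo-based run adds a second ingredient, a placebo-type fill for missed visits, so its result does not correspond exactly to the assumption printed beside it. Missed assessments are foreseen: SAP 4.4.2 names them as a deviation category, and SAP 5.4 covers assessments that could not be completed because of Covid-19.

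**Working it through.** **Planning figures, reproduced.** SAP 4.7 gives effect 0.51 SD, two-sided alpha 0.025, 80% power, 75 completers per arm and 20% dropout. The normal formula gives 74 per arm. The exact t test gives 75 (power 80.4%; 79.8% with 74). Then 75/0.8 = 93.75, so 94 per arm and 188 in total. These figures are not disputed; 0.51 and 20% are used below.

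**Assumed, because the documents do not give them.** Visits missed by participants still in follow-up: 0, 2, 5 or 10% per visit, at random. Within-patient correlation: autoregressive (AR) 0.8, or compound symmetry (CS) 0.6 or 0.4. Treatment effect: 0, 25, 50, 75 and 100% of 0.51 at baseline and Weeks 2, 4, 6 and 8, then constant. Dropout: constant hazard over six visits.

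**One missed Week 10, everything else observed.** The SAP model has k = 5 predictors (baseline and Weeks 2-8); adding Week 12 makes k = 6.
- Residual variance, AR 0.8: 1 − 0.64 = 0.36 from the past only; 0.36/1.64 = 0.22 with Week 12.
- Residual variance, CS, 1 − kρ²/(1 + (k−1)ρ): for ρ = 0.6, 1 − 1.8/3.4 = 0.471 against 1 − 2.16/4 = 0.460; for ρ = 0.4, 0.692 against 0.680.
- Correlation of the imputed Week 10 score with the observed Week 12 score: 0.8 × 0.64 = 0.51 instead of 0.80 (AR 0.8); 0.53 instead of 0.60 (CS 0.6); 0.31 instead of 0.40 (CS 0.4).
- Mean benefit kept when the placebo regression fills the gap: 0.8 × 0.51 = 0.41 SD (AR 0.8). Under CS each predictor has weight ρ/(1 + 4ρ), and the earlier effects sum to 0.51 × 2.5 = 1.275. This gives 1.275 × 0.6/3.4 = 0.23 SD and 1.275 × 0.4/2.6 = 0.20 SD. The participant's own arm has 0.51.

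**Effect on the estimate.** Simulation with 150,000 per arm, forward-only sequential normal regression in place of predictive mean matching, and ANCOVA on the Week 8-12 mean. The comparator fills gaps from the participant's own-arm distribution given all observed visits and uses the placebo regression only after the last observed visit.

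| Correlation | Missed per visit | Gaps among missing Week 8-12 cells | Placebo-based, as written | Placebo-based after dropout only | Excess, % of 0.51 |
|---|---|---|---|---|---|
| AR 0.8 | 0% | 0% | 0.451 | 0.451 | 0.1 |
| AR 0.8 | 2% | 6% | 0.449 | 0.451 | 0.3 |
| AR 0.8 | 5% | 13% | 0.444 | 0.452 | 1.7 |
| AR 0.8 | 10% | 20% | 0.436 | 0.445 | 1.8 |
| CS 0.6 | 0% | 0% | 0.443 | 0.442 | −0.2 |
| CS 0.6 | 2% | 6% | 0.436 | 0.439 | 0.6 |
| CS 0.6 | 5% | 13% | 0.428 | 0.437 | 1.7 |
| CS 0.6 | 10% | 21% | 0.414 | 0.433 | 3.6 |
| CS 0.4 | 0% | 0% | 0.442 | 0.441 | −0.2 |
| CS 0.4 | 2% | 6% | 0.438 | 0.443 | 0.9 |
| CS 0.4 | 5% | 13% | 0.422 | 0.432 | 1.9 |
| CS 0.4 | 10% | 20% | 0.410 | 0.432 | 4.3 |

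The last column uses unrounded estimates. With no missed visits the two procedures are the same, so the 0% rows show simulation noise of up to about 0.2 percentage points.

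The MAR estimate was 0.508-0.514 with past-only predictors and 0.507-0.515 with all observed visits, so gaps at random cause no bias.

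**Scale.** The largest excess is 0.432 − 0.410 = 0.022 SD. With 75 per arm, the standard error of a difference in SD units is about √(2/75) = 0.163, so the excess is about 0.13 of a standard error.

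**The case against.** The strongest reply is that the text can be read as intended. The purpose statement speaks of discontinuation and withdrawal, SAP 4.6 speaks of dropout, and no placebo-based code is printed, so one clarifying sentence might do. That is fair as far as it goes. But the only printed code fills every gap, and SAP 4.6 extends the placebo-based run to all participants. A programmer following the SAP would get the behaviour described.

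Several stronger readings are tempting, and the documents do not support them:

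- *Observed data are discarded.* They are not. Later scores stay in each completed dataset and enter the main model; they are only left out as predictors of the earlier gap.
- *The MAR run is biased.* Not if gaps are random or depend only on earlier scores. What is lost is some precision and within-patient correlation.
- *Missed visits receive placebo values.* The placebo regression is applied to the participant's own earlier scores, so 0.20-0.41 of the 0.51 SD is kept in the example. If the second convergence fallback in SAP 5.1.1.1 were used, only baseline would remain as predictor and that protection would go.
- *The error always works against vafidemstat.* The pull is toward no difference. It counts against the drug only if the drug is better than placebo.
- *These participants are still taking vafidemstat.* Protocol 7.3.5 halts medication when a scheduled platelet count is missed, so someone who misses a whole visit may be off drug for a time. What is certain is that they remain in follow-up, and that is what SAP 4.6 turns on.

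Two mitigations also stand. Imputation follows window mapping, and SAP 4.2 assigns unscheduled assessments to the nearest visit, so a make-up rating can close a gap. With a true benefit, the extra shrinkage is conservative and does not contradict the lower-bound label.

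**Conclusion.** The point holds as a modest correction to the sensitivity analyses. The placebo-based run, as specified, tests a somewhat stricter assumption than the one SAP 4.6 states. With a true benefit of 0.51 SD, the excess pull toward no effect is nil without missed visits, about 0.3-0.9% of 0.51 at 2% missed, 1.7-1.9% at 5% and 1.8-4.3% at 10%. These figures rest on the assumed rates and correlations, on visits missed at random, and on normal regression in place of predictive mean matching.

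A reader might infer that the placebo-based result is uninterpretable or that trial success is at risk. Neither follows. The shift is small against the standard error, and success is decided by the Hochberg procedure on the primary MMRM (SAP 4.6 and 4.12), which is unaffected. The tipping point analysis needs the same clarification, because the SAP does not say which missing cells its adjustment applies to.

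**What to change.** State in SAP 5.1.1.1 that imputation is done in two steps:

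1. Within randomised arm and under MAR, fill gaps before a participant's last observed visit from all observed visits, earlier and later. Keep predictive mean matching (FCS regpmm with all other weeks as predictors), and state a simplification in case the model does not converge.
2. Apply the planned sequential models only to weeks after the last observed visit: within arm for MAR, from the placebo group for MNAR, and with the delta for the tipping point.

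Print the code for the placebo-based run as well. The cost is a few more lines of code and slightly larger imputation models in step 1, which is why the simplification should be stated in advance. No primary test or alpha changes. SAP 4.8 excludes sensitivity analyses from the interim, and Protocol 9.5 allows the SAP to be amended before unblinding.
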